14.6. Data Safety Monitoring Board (DSMB)

All study medication is registered and used in current practice. Despite the known safety profile of the study medications and study design, a DSMB is foreseen.

14.7. Development Safety Update Report

The Coordinating Investigator will provide DSURs once a year throughout the entire duration of the clinical study, or on request, to the Competent Authority (FAMHP in Belgium), Ethics Committee and Sponsor. This DSUR will include all SAE's (who were not categorized as SAR's and were not immediately reported to the EC).

The report will be submitted 1 year (+ maximum 60 days) after the 'Development International Birth Date (DIBD)', and will subsequently be submitted each year until the study is declared ended. This DIBD is the date of the sponsor's first overall authorisation to conduct the clinical trial in any country worldwide. HIRUZ CTU can provide a template that can be used to complete this DSUR.

15. Monitoring/Auditing/Inspection

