There are currently no treatments directed at improving lung repair and local immunity in COVID-19 patients, and no treatment that attempt to halt the progression from manageable acute hypoxic respiratory failure to ARDS. Preventing such progression to ARDS could have a huge impact on the foreseeable overflow of the ICU units. We therefore believe the benefits of administering inhaled GM-CSF treatment in early stage COVID-19 acute hypoxic respiratory failure outweighs the risks associated with a phase 4 IMP administration via a different route and unknown indication.

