14.2.2. SAE reporting

SAE's occurring during the entire study period will be reported as below.

All serious adverse events (initial and follow up information) and pregnancies occurring during this study must be reported by the local Principal Investigator within 24 hours after becoming aware of the SAE to:

- The local ethics committee (it is the responsibility of the local PI to report the local SAE's to the local EC)
- HIRUZ CTU of the University Hospital Ghent
- The National Coordinating Investigator (in case of multicenter studies)
The company Partner Therapeutics that provides the IMP

This reporting is done by using the appropriate SAE form. For the contact details, see below.

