14.4. Flowchart Reporting

Type of Adverse Event	Action to be taken
AE	List all AE's per subject in the patient's file and add this information to the CRF.
SAE	Notify to HIRUZ CTU within 24 hours after becoming aware of the SAE + add the SAE to a list that will be reported yearly (see section 13.8)
SAR	Notify to HIRUZ CTU within 24 hours after becoming aware of the SAE → HIRUZ CTU will submit to the central EC

	→ study team informs company that provides the IMP
SUSAR	Notify to HIRUZ CTU within 24 hours after becoming aware of the SUSAR → HIRUZ CTU will submit to the central EC. → HIRUZ CTU will submit to the FAMHP → study team informs company that provides the IMP

In case the (SU)SAR occurs at a local participating site, the local PI or study team should also contact:

- The local Ethics Committee
- The Co-ordinating Investigator

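### Section 14.7 excludes serious adverse reactions from the annual safety report, so expected ones have no routine written route to the competent authority; separately, 14.2.2 and 14.4 disagree on who receives an SAE

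*Protocol*

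**What the plan says.** Four parts of protocol section 14 bear on this.

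- **14.7 (DSUR).** The report goes once a year, or on request, "to the Competent Authority (FAMHP in Belgium), Ethics Committee and Sponsor". Its content is defined by one sentence: "This DSUR will include all SAE's (who were not categorized as SAR's and were not immediately reported to the EC". It does not say whether the central or the local ethics committee (EC) is meant.
- **14.2.2 (SAE reporting).** All SAEs "must be reported by the local Principal Investigator within 24 hours after becoming aware of the SAE to" four recipients: the local EC, the trial unit (HIRUZ CTU), the National Coordinating Investigator (for a multicentre study) and the company supplying the drug. On the first it adds that "it is the responsibility of the local PI to report the local SAE's to the local EC".
- **14.2.3 (SUSAR reporting).** SUSARs go to the central EC and the FAMHP, within 7 calendar days if fatal or life-threatening and within 15 otherwise.
- **14.4 (flowchart).** For an SAE, the site notifies HIRUZ CTU within 24 hours and must "add the SAE to a list that will be reported yearly (see section 13.8". For a SAR, HIRUZ CTU submits to the central EC and the study team informs the company. Only the SUSAR row adds the step "HIRUZ CTU will submit to the FAMHP". A note below the table adds the local EC and the Co-ordinating Investigator, but only for a SAR or SUSAR at a participating site.

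**The concern.** A cumulative safety report exists so that the authority can see the serious events together, above all those thought to be caused by the drug. As written, 14.7 does the reverse: classing an event as a SAR removes it from the report. The rule looks as if it was drafted from the ethics committee's side, to avoid sending the same event twice. That is an inference, but it would explain the fault, because the DSUR also goes to the FAMHP, which has not already received an expected SAR.

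This matters more here than for a drug in its established use. Section 2.3 describes "administration via a different route and unknown indication" and says that no safety data exist in COVID-19 patients. Safety, as numbers of AEs and SAEs, is the first secondary objective in 3.2.

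The second problem is practical. A site with an SAE that it judges unrelated finds one list of recipients in the text and a shorter one in the flowchart, and cannot comply with both as complete instructions.

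**Working it through.** The plan states no figure on this point, so the check traces each class of serious event through every written route.

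**Step 1. Classes.** Section 14.1 defines a SAR as a serious event believed with reasonable probability to be due to study treatment, and a SUSAR as a SAR that is also unexpected. A SUSAR is therefore a SAR. This leaves three classes: unrelated SAE, expected SAR, SUSAR.

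**Step 2. Routes to the FAMHP.**

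| Class | Expedited (14.2.3, 14.4) | DSUR (14.7) |
|---|---|---|
| Unrelated SAE | No | Yes, if the EC in 14.7 is the central EC; no, if it is the local EC |
| Expected SAR | No: the SAR row has no FAMHP step | No: categorized as a SAR |
| SUSAR | Yes, 7 or 15 days | No: a SUSAR is a SAR |

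The expected SAR row has no entry in either column. The DSUR column holds at most one class of three, the one judged unrelated to the drug.

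**Step 3. Is the exclusion only loose grammar?** The parenthesis in 14.7 could be read leniently, as if it meant that SAEs not classed as SARs are included too. The flowchart points the other way: only its SAE row carries a yearly list, and the SAR and SUSAR rows carry none. The two sections agree with each other on the literal reading.

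**Step 4. Recipients of an unrelated SAE.**

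| Recipient | 14.2.2 | 14.4, SAE row |
|---|---|---|
| HIRUZ CTU | Yes, 24 hours | Yes, 24 hours |
| Local EC | Yes, 24 hours | Not named |
| National Coordinating Investigator | Yes, 24 hours | Not named |
| Company | Yes, 24 hours | Not named |
| Yearly list | Not named | Yes, citing 13.8 |

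Three of the four recipients in 14.2.2 are missing from the flowchart row (4 − 1 = 3).

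**Step 5. The cross-reference.** Section 13 covers data handling and ends at 13.4. The only section on yearly safety reporting is 14.7. The reference to 13.8 is probably left over from renumbering.

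**Step 6. Which EC.** If 14.7 means the local EC, then 14.2.2, which sends every SAE there within 24 hours, would leave the DSUR with no events. If it means the central EC, which 14.4 names for HIRUZ CTU's submissions and 16.3.1 designates, unrelated SAEs stay in. The text must say which.

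Steps 2 and 4 are separate faults. The mismatch in step 4 does not cause the gap in step 2, which comes from the DSUR exclusion combined with a SAR row that has no FAMHP step.

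**The case against.** The strongest reply is that no SAR is lost. Under 14.4 every SAR goes to HIRUZ CTU within 24 hours, then to the central EC and the company, and from a participating site also to the local EC and the Co-ordinating Investigator. The FAMHP may also ask for a DSUR at any time. This stands, and it rules out saying that expected reactions never reach the authority or would go unseen until the final analysis. It does not remove the fault: a DSUR supplied on request would follow the same content rule, and what is missing is the routine route.

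A reader might infer four stronger points that the protocol does not support.

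- **That the DSMB receives no events.** Sections 14.2, 14.4 and 14.7 do not name it, and 14.6 says only that one is foreseen. That is silence: data flow to a DSMB is commonly set in a charter, and the contact list in 14.3 is not available for review.
- **That a side effect listed in 8.1.8, such as bronchospasm, is a worked example of an unreported event.** Section 14.1 judges expectedness against the SmPC or the investigator's brochure, and neither is visible. Serious bronchospasm after inhalation might be a SUSAR, which does go to the FAMHP.
- **That the DSUR would be empty.** This holds only on the local-EC reading in step 6 and cannot be asserted.
- **That the first DSUR falls due too late for the 30-week study estimated in 5.3.** The DSUR interval runs from first authorisation and the 30 weeks is an estimate of study length, so the clocks differ. The current version is dated June 2021, more than a year after version 2.0, so the estimate may be out of date. A report falling due after a short trial also follows from its being annual and is not a drafting error.

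**Conclusion.** The point holds as a fault in the written rules. Followed exactly, 14.7 produces a cumulative report without any event judged related to the drug. With 14.2.3 and 14.4, it leaves expected SARs with no routine written route to the FAMHP, and it omits SUSARs from the cumulative report although they are sent singly. Separately, 14.2.2 and 14.4 give conflicting recipients for an unrelated SAE, and the yearly list refers to a section that does not exist.

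The size is a count of classes and recipients: at most one of three event classes in the DSUR, one class with no routine route to the authority, and three of four recipients missing from the SAE row. How many patients this touches cannot be derived from the protocol, which gives no expected rate of SARs.

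The conclusion rests on the literal wording of 14.7, supported by the flowchart, and on the protocol alone. A separate safety procedure could fill the gap in practice, but the protocol text would still be wrong. The primary endpoint analysis is not affected.

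**What to change.** 1. **14.7.** Replace the content sentence with one stating that the DSUR lists all SAEs cumulatively, including those classed as SARs or SUSARs, whether or not they have already been reported to an ethics committee.
2. **14.4.** Add the 14.2.2 recipients to the SAE, SAR and SUSAR rows, and keep the central EC and FAMHP steps already there. Replacing the rows with the 14.2.2 list would make matters worse: 14.2.2 names neither the central EC nor the FAMHP, so the SAR row would lose the first and the SUSAR row both.
3. **14.2.2, 14.4 and 14.7.** State in each place whether the central or the local EC is meant.
4. **14.4.** Change the cross-reference from 13.8 to 14.7.

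The cost is a wording amendment, approved as 16.3.2 requires, and a longer yearly listing. HIRUZ CTU already receives every event concerned within 24 hours, so no new data are collected and no treatment rule changes.

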15.1. Monitoring

15.1.1. General

Monitoring of the study will be performed in compliance with GCP E6(R2) and the applicable regulatory requirements. The study team will be trained in an initiation visit by the monitor. A training and delegation log will be held. A detailed description of the monitoring tasks can be found in the latest version of the (study-specific) 'Monitoring plan'.

15.1.2. Monitoring team

Monitoring services will be provided by HIRUZ CTU. All relevant contact details (e.g. primary contact person, can be found in the 'Monitoring plan'.

15.1.3. Scope

Monitoring services will consist of the following (non-exhaustive list):

- review of informed consents and the followed process
- check on recruitment status
- checking for protocol deviations/violations
- checking GCP compatibility
- check on safety reporting compliance
- IMP handling and storage
- review of study data

...

15.2. Inspection

This study can be inspected at any time by regulatory agencies during or after completion of the study. Therefore access to all study records, including source documents, must be accessible to the inspection representatives. Subject privacy must be respected at all times, in accordance to GDPR, GCP and all other applicable local regulations.

The investigator/study team should immediately notify the sponsor if he or she has been contacted by a regulatory agency concerning an upcoming inspection.

15.3. Protocol Deviation policy

Sponsor and all investigators agree to take any reasonable actions to correct protocol deviations/violations noted during monitoring/inspection, in consultation with the monitoring team. All deviations must be documented on a protocol deviation log by the study team that is kept available at any time for monitoring/inspection purposes. Under emergency circumstances, deviations from the protocol to protect the rights, safety or well-being of human subjects may proceed without prior approval of the sponsor and the EC.

15.4. Serious breach to GCP and/or the protocol

Critical issues that significantly affect patient safety, data integrity and/or study conduct should be clearly documented and will be communicated with the Coordinating Investigator, HIRUZ CTU and possibly both the applicable Ethics Committee(s) and Competent authority. (Please contact HIRUZ CTU asap in case of a serious breach: [contact] and/or [name]).

Early determination of the study (in a specific center or overall) may be necessary in case of major non-compliance.

16. Ethical and legal aspects

16.1. Good Clinical Practice

The study will be conducted cfr the latest version of the ICH E6 (R2) GCP guidelines, creating a standard for the design, conduct, performance, monitoring, auditing, recording, analyses and reporting of clinical studies that provides assurance that the data and reported results are accurate and that the rights, integrity and confidentiality of study subjects are protected.

16.2. Informed Consent

Eligible subjects may only be included in the study after providing written (witnessed, if needed) Ethics Committee-approved informed consent, or, if incapable of doing so, after such consent has been provided by a legally acceptable representative(s) of the subject.

Informed consent must be obtained before conducting any study-specific procedures (as described in this protocol).

Prior to entry in the study, the investigator must explain to potential subjects or their legal representatives the study and the implication of participation. Subjects will be informed that their participation is voluntary and that they may withdraw consent to participate at any time. Participating subjects will be told that their records may be accessed by competent authorities and by authorized persons without violating the confidentiality of the subject, to the extent permitted by the applicable law(s) and/or regulations. By signing the Informed Consent Form (ICF), the subjects or legally acceptable representatives are authorizing such access.

After this explanation and before entry to the study, written, dated and signed informed consent should be obtained from the subject or legally acceptable representative. The ICF should be provided in a language sufficiently understood by the subject. Subjects must be given the opportunity to ask questions.

The subject or legally acceptable representative will be given sufficient time to read the ICF and to ask additional questions. After this explanation and before entry to the study, consent should be appropriately recorded by means of either the subject's or his/her legal representative's dated signature or the signature of an independent witness who certifies the subject's consent in writing. After having obtained the consent, a copy of the ICF must be given to the subject.

In case the subject or legally acceptable representative is unable to read, an impartial witness must attest the informed consent.

Subjects who are unable to comprehend the information provided or pediatric subjects can only be enrolled after consent of a legally acceptable representative.

The following information should be added to the electronic patient dossier (EPD):

- which version of the ICF was obtained
- who signed the ICF
- if sufficient time has been given to consider participation into the study
- which investigator obtained ICF with the date of signature
- if a copy was provided to the patient
- start and end of participation in the study

16.3. Approval of the study protocol

16.3.1. General

The protocol has been reviewed and approved by the Ethics Committee of the Ghent University (Hospital), designated as the central Ethics Committee, after consultation with the local Ethics Committees, and the Federal Agency for Medicine and Health Products (FAMHP). This study cannot start before both approvals have been obtained.

16.3.2. Protocol amendments

Any significant change or addition to the protocol can only be made in a written protocol amendment that must be approved by the Central Ethics Committee (and the FAMHP if applicable).

Only amendments that are intended to eliminate an apparent immediate safety threat to patients may be implemented immediately.

Notwithstanding the need for approval of formal protocol amendments, the investigators are expected to take any immediate action, required for the safety of any subject included in this study, even if this action represents a deviation from the protocol. These actions should always be notified to the sponsor.

16.4. Confidentiality and Data Protection

All study data will be handled in accordance with the law on General Data Protection Regulation (GDPR) and institutional rules

[Belgian law dated on 30 July 2018 and 22 Aug. 2002].

The collection and processing of personal data from subjects enrolled in this study will be limited to those data that are necessary to fulfill the objectives of the study. These data must be collected and processed with adequate precautions to ensure confidentiality and compliance with applicable data privacy protection laws and regulations.

Appropriate technical and organizational measures to protect the personal data against unauthorized disclosures or access, accidental or unlawful destruction, or accidental loss or alteration must be put in place. Sponsor and site personnel whose responsibilities require access to personal data agree to keep the identity of subjects confidential.

The informed consent obtained from the subject includes explicit consent for the processing of personal data and for the investigator/institution to allow direct access to his or her original medical records (source data/documents) for study-related monitoring, audit, Ethics Committee review and regulatory inspection. This consent also addresses the transfer of the data to other entities, if applicable.

Privacy and confidentiality of data generated in the future on stored samples will be protected by the same standards applicable to all other clinical data.

Stored samples will be pseudonymized throughout the sample storage and analysis process and will not be labeled with personal identifiers.

16.5. Liability and Insurance

The sponsor has taken a no fault insurance for this study, in accordance with the relevant legislation (article 29, Belgian Law of May 7, 2004).

Sponsor: Ghent University Hospital

Insurance Details: Allianz Global Corporate & Specialty; [name]; [contact]

Polis number: BEL000862

Appendix 1: USPI (US Package insert)
